Protocol Full Title: DASH Cloud: Using digital health to improve adherence to the DASH diet among women at risk for cardiovascular disease

Short Title: DASH Cloud

Purpose of the Study

One-third of women have hypertension (HTN), and the risk of cardiovascular disease (CVD) because of HTN is more serious among women than men. Until recently, however, efforts to reduce CVD mortality focused primarily on men. The DASH diet is a proven behavioral strategy to reduce blood pressure, however, national adherence rates are poor. Using digital health tools may help to improve adoption of the DASH diet.

Digital health approaches capitalize on the ubiquitous utilization of mobile technologies and have broad dissemination potential. There have been few efforts to test a DASH intervention via digital health and none directed to women. This proposal will leverage a commercial diet tracking application and our existing intervention technology platform to test the feasibility of DASH Cloud, a digital health intervention for women with pre-hypertension and hypertension. The primary outcome is DASH diet adherence.

Background and Significance

Women need better interventions for hypertension self-management. One-third of and pre and postmenopausal women have hypertension¹ and only half of those women have their blood pressure under control. Uncontrolled blood pressure is the strongest predictors of heart disease – the leading cause of death among women. This is because heart disease is more serious among women than men. After a heart attack, women have lower survival rates and a poorer quality of life. Despite these gender-based differences in outcomes, our understanding is limited about how to address the unique issues that women face in managing hypertension behaviorally. Developing behavioral interventions specifically for women in the pre- and postmenopausal period is critical to alleviating the burden of hypertension and heart disease among women.

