mobile technologies. Our work is unique because we go beyond simply sending tips or reminders. Rather, our interventions prescribe tailored behavior change goals, prompt tracking of these goals via mobile technologies and then send immediate tailored feedback. As a result, we have been successful in achieving high rates of tracking adherence^{17,20} I aim to leverage my experience working on digital health intervention trials to improve adherence to the DASH diet among women with hypertension.

This study will have several areas of impact. We will establish the feasibility of a novel digital health-based approach for disseminating the DASH diet for women, using Nutritionix, a commercially available diet tracking app that thousands of Americans are already using. The data from this pilot feasibility trial will set the foundation for a larger, fully-powered R01 grant to examine whether DASH Cloud can improve blood pressure outcomes among women with hypertension. This proposal will focus on the following specific aims.

Aim 1: To modify existing technology platforms and develop content for the DASH Cloud intervention for women with hypertension or pre-hypertension.

Aim 2: To test the feasibility of the DASH Cloud intervention compared to education control among women with hypertension or pre-hypertension (n=up to 65) via a 3-month randomized controlled trial.

- Utilization of intervention components – daily diet tracking rates, and clicks to skills training materials.
- Change in dietary patterns – 3-month change in DASH diet adherence score (as measured from 24-hour recalls)
- Acceptability - patient satisfaction and intention for continued use as measured by surveys.

Aim 3: To evaluate the preliminary efficacy of the DASH Cloud intervention relative to education control on blood pressure, weight, and medication adherence at 3 months.

Design and Procedures

Study Design

We will enroll up to 200 adult women aged 21-70 with pre-hypertension or hypertension in order to qualify up to 65 to be randomized in a 3-month randomized controlled trial to test the initial feasibility of *DASH Cloud*, a digital health intervention for women with HTN. More details are described below.

Selection of Subjects

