Setting: We will recruit community participants from the Durham, NC area. Using designated space at the Sarah W. Stedman Center for Nutrition and Metabolism at Duke and Duke Digital Health, participants will complete baseline and follow-up visits where they will complete physiological and survey-based data collection.

Sample: We will randomize participants to either the DASH Cloud intervention or to DASH Light_education control and follow up at 3 months.

Inclusion/Exclusion:

Inclusion: ages 21-70 years; BMI >18.5 kg/m²; on self-reported use antihypertensive medication or self-reported systolic blood pressure 120-159 mmHg and/or diastolic blood pressure of 80-99; current use of a smartphone with an updated operating system, data plan, willingness to be texted daily or weekly; an active email account; spoken and written English fluency.

Exclusion: CVD event in prior 6 months; active malignancy; active psychosis or recent psychiatric institutionalization; current pregnancy or lactation; current participation in a similar trial.

Subject Recruitment and Compensation

We will recruit participants using a multi-pronged strategy: 1) we will distribute flyers at local gyms, community centers, grocery stores, and health and wellness stores; 2) we will collaborate with Duke Early Phase Clinical Research (formerly DCRU) and the Duke Primary Care Research Consortium (PCRC) to request that they query their database for subjects who fit the inclusion/exclusion criteria and email them information about the study, including a link to the study websites (dashcloud.org or dashcloudstudy.com). These URLs do not contain study information, rather they just redirect participants to the REDCap screening survey; 3) we will use social media (Twitter and Facebook) to advertise the study and direct interested subjects to the study web site, and; 4) we will email community organizations, including local health departments and churches, information about the study, including a link to the study web site. 5) We will use the contact list for participants who were ineligible for Study D0822 Comparing Self-Monitoring Strategies for Weight Loss (Campus IRB) that acknowledged they were interested in being contacted for other studies. 6) We will use ResearchMatch.org to connect with potentially eligible subjects. We have used these methods successfully in many of our team's previous studies.

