- 1) Diet tracking: proportion of participants completing daily dietary self-monitoring
- 2) Review of skills training: number of clicks to skills training via video tracking software.

DASH adherence: Dietary intake data will be collected using NCI's Automated Self-Administered 24-hour Recall tool (<https://asa24.nci.nih.gov/>). Participants will be prompted via email by study staff to complete the ASA-24. We will collect 2 dietary recalls at baseline and 3 months. To determine DASH adherence, we will use a previously determined index based on 11 food groups (e.g., fruits) and nutrients (e.g., sodium). We have experience using the ASA-24 in a previous trial with much success.

Patient satisfaction: We will use measures that we have delivered successfully in prior studies.

Blood pressure: Blood pressure will be measured at baseline and 3 months in the upper arm in triplicate at 1-minute intervals. Measurements will be obtained by trained study staff using the validated Omron HEM-907XL blood pressure monitor.

Sociodemographics: We will collect self-reported age, race/ethnicity, health insurance, income, employment status, education, current health status, household size, and marital status at baseline only.

Risk/Benefit Analysis

The primary risk to the subject is loss of confidentiality. The mobile technology carries a higher risk of this than the other stored data due to the nature of mobile technology and the servers used to deliver the intervention. We will follow data security plans used in our previous and current studies, which were developed with the guidance of Duke Office of Information Security. The details are explained below in the data and safety monitoring section.

Potential benefits for study participants include improved blood pressure and consequent reduction in cardiovascular risk. An additional benefit for some participants may be personal satisfaction in being part of a study that may have major public health implications for the community. No benefit from participation can be guaranteed. Potential benefits to others include the possibility that this research will help researchers evaluate the feasibility and efficacy of the DASH Cloud system in promoting DASH diet adherence. The minimal health risks to participants listed above are offset by the potential benefits to them and to society.

Cost to the Subject

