No costs are incurred by the subject, unless the subject is charged for receiving text messages or data usage for watching videos. This is very uncommon, and if it occurs, the cost is typically less than 3 cents per text received.

Data Analyses and Statistical Considerations

We will perform descriptive analyses to determine engagement and feasibility. Linear mixed modeling will be used to test for across group differences in DASH adherence and other secondary outcomes. Our model will

include group, time, and a group by time interaction, and will be fitted with a full maximum likelihood method using all data. As this is a feasibility study, we have estimated sample size from our previous text messaging trial where we saw strong engagement; 50% texted daily and 85% texted at least 2 days/week.

Data and Safety Monitoring

Study records that identify patients will be kept confidential as required by law. All data will be marked with a unique code number for storage at Duke University Health System in accordance with Duke's Institutional Review Board's guidelines and policies. All data collection will occur in private settings where patient survey responses cannot be seen or heard by others. Patients can refuse to answer any of the questions or stop participation in this study at any time.

Mobile technology: Information collected by Nutritionix mobile app is subject to the terms of use. Many apps make claims that they are secure, compliant with federal privacy regulations, and used and tested by other academic centers. However, any mobile app that is downloaded carries potential security risks, and Duke cannot guarantee that these mobile apps are free of risk. Some apps may be able to perform hidden functions or may have security flaws that allow unauthorized access to information. We are unable to fully tell participants what information these mobile apps can access or change on their phone or what information from their phone may be stored outside of Duke. Participants will be encouraged to limit personal identifiers entered into mobile applications only to those that they wish to voluntarily share with others.

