IRB Pro00081972
Version 11/06/17

Data Analyses and Statistical Considerations

We will perform descriptive analyses to determine engagement and feasibility. Linear mixed modeling will be used to test for across group differences in DASH adherence and other secondary outcomes. Our model will include group, time, and a group by time interaction, and will be fitted with a full maximum likelihood method using all data. As this is a feasibility study, we have estimated sample size from our previous text messaging trial where we saw strong engagement; 50% texted daily and 85% texted at least 2 days/week.

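### Full maximum likelihood in at most 65 women makes standard errors and p-values for the group-by-time test slightly too small; REML with t-based inference avoids this at almost no cost.

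*SAP*

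**What the plan says.** The SAP and the protocol carry the same analysis text under Data Analyses and Statistical Considerations.

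- **Purpose of the model (SAP):** "Linear mixed modeling will be used to test for across group differences in DASH adherence and other secondary outcomes".
- **Fixed effects (SAP):** "Our model will include group, time, and a group by time interaction".
- **Estimator:** the SAP says the model "will be fitted with a full maximum likelihood method using all data". The protocol says it will "include group, time, and a group by time interaction, and will be fitted with a full maximum likelihood method using all data".
- **Size (Protocol, Study Design):** women are enrolled "in order to qualify up to 65 to be randomized in a 3-month randomized controlled trial".
- **Arms (Protocol, Selection of Subjects):** "We will randomize participants to either the DASH Cloud intervention or to DASH Light_education control and follow up at 3 months".
- **Timing (Protocol, Measures):** "We will collect 2 dietary recalls at baseline and 3 months". Blood pressure is measured at the same two visits.
- **Status of the outcome (Protocol, Purpose of the Study):** "The primary outcome is DASH diet adherence".

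Neither document gives a significance level, a reference distribution for the test (t, normal or likelihood ratio), a degrees-of-freedom method, another small-sample correction, or a covariance structure. Neither gives a reason for choosing ML, such as a planned likelihood-ratio comparison.

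**The concern.** ML estimates the variance components as if the fixed effects were known. The variance estimates are then too low by an amount that grows as the sample shrinks. In a trial of at most 65 women this can be seen, though it is small.

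The direction is known. Standard errors and p-values are too small and confidence intervals too narrow, so every between-group comparison from this model leans slightly towards a difference. That covers DASH adherence and the outcomes of Aim 3 analysed in the same way. The protocol intends these data as groundwork for a fully powered trial, so the error bars should be right even where no formal decision hangs on them.

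**Working it through.** The plan gives no alpha, power, effect size, SD or dropout rate for this test, so it has no figure to reproduce. The check asks how far ML moves the standard error and the type I error.

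**Inputs from the documents:** two arms, two visits, at most 65 women, fixed effects for group, time and their interaction, ML estimation.

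**Assumptions not in the documents:** two-sided 5% level; one score per woman per visit; random-intercept covariance with an intercept variance estimated above zero, or unstructured covariance; 40 to 65 women with both visits.

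**1. Standard error.** With complete data at two visits, the group-by-time estimate is the between-arm difference in mean change. ML estimates the variance of the changes as SS/n and REML as SS/(n − 2). Hence

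SE(ML)/SE(REML) = √((n − 2)/n) = √(63/65) = 0.9845.

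The ML variance is 2/65 = 3.1% too small and the standard error 1.55% too small.

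**2. Type I error.** Let t be the correct statistic, with n − 2 degrees of freedom. The true error rate is the exact two-sided t tail beyond the value of |t| at which each method rejects:

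- ML with t: critical value t(0.975, n − 2) × √((n − 2)/n)
- ML with z: 1.96 × √((n − 2)/n)
- REML with z: 1.96
- ML likelihood-ratio test: √((n − 2)(exp(3.8415/n) − 1)), which at n = 65 is √(63 × (exp(3.8415/65) − 1)) = 1.958

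| Women with both visits | SE ratio | ML + t | Likelihood ratio | ML + z | REML + z | REML + t |
|---|---|---|---|---|---|---|
| 65 | 0.9845 | 5.35% | 5.46% | 5.82% | 5.44% | 5.00% |
| 55 | 0.9816 | 5.42% | 5.55% | 5.97% | 5.53% | 5.00% |
| 40 | 0.9747 | 5.58% | 5.77% | 6.37% | 5.74% | 5.00% |

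**3. Share due to ML.** At n = 65 the excess with ML and z is 5.82 − 5.00 = 0.82 points. REML with z already has 5.44 − 5.00 = 0.44 of these, so just over half comes from the normal reference. ML with the correct t reference adds 0.35 points.

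**4. What would be printed.** At n = 65 a correct p of 0.050 appears as 0.047 under ML with t, or 0.042 under ML with z. A 95% interval is too narrow by 1.55% (ML with t), 1.92% (REML with z) or 3.44% (ML with z).

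**5. Incomplete data.** The rows for 55 and 40 use completers only, whereas the plan keeps all records. The planned random-intercept model was therefore simulated with 65 women, correlation 0.5, no true effect and data missing completely at random. Each setting had 11,126 to 11,946 trials (Monte Carlo SE 0.2 points), with t on completers minus 2 degrees of freedom.

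| Women with baseline only | SE ratio | ML + t | REML + t | Difference (same datasets) |
|---|---|---|---|---|
| 0 | 0.9845 | 5.14% | 4.85% | 0.29 points |
| 10 | 0.9825 | 5.04% | 4.67% | 0.37 points |
| 25 | 0.9780 | 5.64% | 5.09% | 0.55 points |

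A separate simulation with correlation 0.3 and dropout of 0%, 10% and 20% (4,000 trials each) gave SE ratios of 0.9845, 0.9834 and 0.9821.

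**The case against.** The strongest reply is that this hardly matters. ML alone costs about 0.35 points of type I error with 65 complete cases. In the simulation, ML with t rejected 5.14% and 5.04% of the time with 0 and 10 women lost, within Monte Carlo error of 5%. The trial is a feasibility study with no stated alpha or success threshold, so 0.047 in place of 0.050 decides nothing. The protocol's Measures section also names use of the intervention components as the primary feasibility outcome, and that is analysed descriptively. All of this stands as a limit on importance. It does not make the standard error right, and the ML and REML rates come from the same datasets, where ML rejected more often in every setting.

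Second, the larger figures come from the normal reference, which the plan does not specify, and REML alone would not cure that. This is correct: in the simulation the ML likelihood-ratio test (5.26%, 5.23%, 5.91%) was almost level with REML plus z (5.22%, 5.24%, 5.91%). The remedy must therefore name the t reference as well as the estimator.

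Third, ML is a legitimate estimator and is needed for likelihood-ratio tests of fixed effects. That is true, but no such test is mentioned, and here it would itself run at 5.46%. Nor is ML needed to keep incomplete records, since REML keeps them too.

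Fourth, n against n − 2 presumes one score per visit, while two recalls are collected. If both entered a random-intercept model separately, the ratio at n = 65 would be √(193/195) = 0.995 and the type I error with t 5.12%. The bias shrinks but neither vanishes nor reverses. One adherence score per visit is the more natural reading.

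**Conclusion.** The concern holds, as a minor point. As written, the plan prescribes an estimator that understates the standard error of its only between-group test, with no correction. With 65 complete cases and one score per visit, the standard error is 1.55% too small. At an assumed two-sided 5% level the type I error is 5.35% with t or 5.46% by likelihood ratio. With an assumed 10 or 25 women lost after baseline, the ML standard error is 1.75% or 2.2% below the REML one, and ML adds about 0.4 or 0.55 points to the type I error. Figures near 6% arise only if a normal reference is also used. Only borderline results would change.

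**What to change.** In Data Analyses and Statistical Considerations of both the SAP and the protocol, replace the full maximum likelihood wording with: *restricted maximum likelihood (REML) with Kenward-Roger or Satterthwaite degrees of freedom and t-based 95% confidence intervals, using all available data.*

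Both parts are needed, because REML with a normal reference still gives 5.44% at n = 65. The single group-by-time term can be tested by its t statistic from the REML fit, so no likelihood-ratio comparison is required. It would help to state in the same place whether the two recalls are averaged to one score per visit, because the degrees of freedom depend on it.

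The cost is one phrase in each document and one software option. No further participants or data are needed; intervals become slightly wider.
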